11.1 Serious Adverse Events

A Serious Adverse Event (SAE) is any adverse event that, at any dose:

Results in death.

- Is life threatening
 - > The term "life-threatening" in the definition of "serious" refers to an event in which the subject was at risk of death at the time of the event. It does not refer to an event, which hypothetically might have caused death, if it were more severe.
- Requires hospitalization or prolongation of an existing hospitalization.
 - > The following hospitalizations will **not** be considered serious:
 - Preplanned (before study) hospital admissions, unless the hospitalization is prolonged.
 - Planned admissions (as part of the study, e.g. routine biopsies).
 - Re-hospitalizations lasting less than 24 hours.
 - Emergency room visits.
 - Hospitalizations for elective surgery for a pre-existing condition. If untoward event occurs during an elective procedure, its occurrence must be reported as an AE, either serious or non-serious, according to the usual criteria.
- Results in persistent or significant disability/incapacity
 - The term disability means a substantial disruption of a person's ability to conduct normal life functions. This definition is not intended to include experiences of relatively minor medical significance, such as uncomplicated headache, nausea, vomiting, diarrhea, influenza, and accidental trauma (e.g., sprained ankle) which may interfere or prevent everyday life functions but do not constitute a substantial disruption.
- Is a congenital anomaly/birth defect.

CONFIDENTIAL

Any medically significant events that may require medical or surgical intervention to prevent one of the outcomes listed above.

11.1.1 Serious adverse event collection and reporting

It is the Investigators responsibility to report all SAEs (including all secondary efficacy outcomes) that occur from signing of informed consent and randomization through Day +37 by entering serious adverse events data into the InformTM EDC system within 24 hours of becoming aware of the SAE; the SAE must be followed through resolution or stabilization.

• Consented patients that withdraw from the study **prior** to randomization and experiences an SAE, the event must be followed (data collection) through the completion of the screening Encounter 1 or 2 and the completion of the screening eligibility eCRF.

11.1.2 Lack of Efficacy

Lack of efficacy **will not** be reported as study drug related. The signs and symptoms or clinical sequelae resulting from lack of efficacy will be reported only if they fulfill the SAE definitions.

11.1.3 Clinical or Laboratory Abnormalities

Abnormal laboratory findings or other abnormal assessments that are judged by the investigator as clinically significant will be recorded as SAEs if they meet the definition. Clinically significant abnormal laboratory findings or other abnormal assessments that are detected during the study or are present at baseline and significantly worsen following the start of the study will be reported as SAE.

11.1.4 Assessment of Causality

- Drug-related means that there is a reasonable possibility that the adverse event may have been caused by the test agent.
- The investigator is obligated to assess the relationship between investigational product and the occurrence of each SAE.
- Causality will be assessed as
 - Unlikely related: An event for which an alternative explanation is more likely e.g., concomitant drug(s), concomitant disease(s), and/or the relationship in time suggests that a causal relationship is unlikely.
 - Likely related: An event that might be due to the use of the drug. An alternative explanation is less likely e.g., concomitant drug(s), concomitant disease(s). The relationship in time is suggestive (e.g., confirmed by dechallenge).

The Investigator should use clinical judgment to determine the relationship. Alternative causes such as natural history of the underlying diseases, concomitant therapy, other risk factors, and the temporal relationship of the event to the investigational product will be considered and investigated. The degree of certainty with which an event is attributed to investigational product will be determined by how well the event can be understood in terms of one or more of the following:

- known pharmacology (including half life) of the study drug.
- any reaction of a similar nature previously observed with this drug or class of drugs.
- reports in the literature of the experience as related to this drug or class of drugs.

- the temporal relationship of the experience with drug infusion, termination of the event with withdraw of the drug, or reproduction of the event on repeat challenge with the drug.
- **11.1.5** Unexpected Adverse Events are those that have not been listed in the:
 - Package insert for a given drug or investigator's brochure (for FDA investigational agents);
 - Protocol; or
 - Informed consent document.

Note: that expected events listed in the protocol are based on participant characteristics, take into account the nature of the intervention (if any), and include events that might reasonably be expected to occur in the study population but do not bear on the safety of the study.

- **11.1.6** Unanticipated Problem: According to OHRP (Office for Human Research Protections), unanticipated problems generally include any incident, experience, or outcome that meets all of the following criteria:
 - unexpected (in terms of nature, severity, or frequency) given (a) the research procedures that are described in the protocol-related documents, such as the IRB-approved research protocol and informed consent document; and (b) the characteristics of the subject population being studied;
 - related or possibly related to participation in the research (in this guidance document, *possibly related* means there is a reasonable possibility that the incident, experience, or outcome may have been caused by the procedures involved in the research); and
 - suggests that the research places subjects or others at a greater risk of harm (including physical, psychological, economic, or social harm) than was previously known or recognized.

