6.3 Potential Adverse Reactions related to Study Drug Administration

6.3.1 Dalteparin

The main adverse reaction associated with administration of dalteparin, as with other parenteral anticoagulants, is bleeding. In the context of the BRIDGE trial, bleeding if it occurs is likely (in approximately 80-90% of cases) to occur at the site of the surgery/procedure. Major bleeding, which is a more serious form of bleeding that may require blood transfusion, re-operation or other medical treatment, is an outcome that may occur in approximately 3% of patients. The BRIDGE trial will closely monitor patients for this outcome and if it occurs, patients will receive

CONFIDENTIAL

prompt medical treatment. Other adverse reactions associated with the administration of dalteparin are listed below as are the approximate risk for these adverse outcomes:

6.3.1.2 Possible (≥10%)

- bruising or bleeding at injection site
- discomfort or pain at injection site

6.3.1.3 Unlikely (<10%)

- elevation in liver enzymes (typically resolves after stopping LMWH, including dalteparin)
- mild allergic reaction (skin rash)
- infection at injection site

6.3.1.4 *Rare* (≤1%)

- heparin induced thrombocytopenia (associated with stroke, myocardial infarction, venous thromboembolism, limb gangrene, amputation or death)
- epidural hematoma with possible paralysis in patients receiving dalteparin *during* spinal anesthesia
- severe allergic reaction (angioedema, anaphylaxis)

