11.1.7 Follow-up of SAEs

- All SAEs will be followed until resolution, until the condition stabilizes, until the event is otherwise explained, or until the D +37 follow-up visit, whichever occurs first.
- As additional information pertaining to an SAE becomes available, the eSAE form should be updated and resubmitted within 1 business day of knowledge of the information.

11.1.8 DCRI Safety Surveillance and Medical Monitor:

- DCRI Safety Surveillance will be notified of SAEs via email and will print the SAE form from the electronic data capturing system.
- DCRI Safety Surveillance will perform a clinical review of all SAE reports to verify that all sections are complete and consistent.
- DCRI Safety Surveillance will query for incomplete information, data clarification, and/or follow-up information within the Inform database.
- DCRI Safety Surveillance will write a clinical narrative of the event, enter the data into the Clintrace safety database and code the event using the current MedDRA dictionary.
- The DCRI Medical Monitor will review all SAEs, the MedDRA coding and assess the event for "expectedness" per the dalteparin product label.
- DCRI Safety Surveillance will forward the SAE report, a copy of the narrative, a copy of any queries sent to the site, and the Medical Monitor's assessment to [name], and the DSMB chair within 1-2 business days of initial receipt. A copy of the above documents

CONFIDENTIAL

will be forwarded to Eisai for SAEs assessed by the site investigator as "likely related" to study drug.

 SAEs will be reported to NHLBI according to current NHLBI Adverse Event and Unanticipated Problem Reporting Policy. The NHLBI Project Officer will be provided with a copy of the SAE report for all fatal, life-threatening, or unexpected serious adverse events that are likely related to study participation within 7 calendar days. All unanticipated problems will be reported to NHLBI within 30 calendar days.

11.1.9 Regulatory Reporting

All SAEs which are assessed as unexpected by the Medical Monitor and associated with the use of the study drug (likely related) by the Site Investigator require expedited reporting to the FDA and/or Health Canada. For these events, DCRI Safety Surveillance will generate CIOMS forms and forward them to [name] for review and to DCRI Regulatory Services for submission. DCRI Safety Surveillance and Medical Monitor will provide an Investigator Alert packet for distribution to investigative sites.

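### The two causality ratings in section 11.1.4 do not match that section's own definition of drug-related, so some SAEs may miss supplier forwarding or expedited reporting

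*Combined protocol and SAP*

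**What the plan says.** Section 11.1.4 (Assessment of Causality) has three parts that bear on this point.

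- **Definition.** Drug-related "means that there is a reasonable possibility that the adverse event may have been caused by the test agent".
- **Lower rating.** *Unlikely related* is "An event for which an alternative explanation is more likely". Other drugs and other diseases are given as examples, and timing that argues against the drug also counts.
- **Upper rating.** *Likely related* begins "An event that might be due to the use of the drug" and continues "An alternative explanation is less likely", with suggestive timing.

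There is no middle level. The section adds: "The Investigator should use clinical judgment to determine the relationship". It lists pharmacology, class experience, literature and timing as considerations, and sets no numeric threshold.

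The upper rating is then a reporting trigger. Under 11.1.8, the supplier receives only the SAEs that the site investigator rates *Likely related*. Under 11.1.9, SAEs that the Medical Monitor finds unexpected and that are "associated with the use of the study drug (likely related) by the Site Investigator require expedited reporting" go to FDA and/or Health Canada. Separately, 11.1.8 sends SAE reports to the DSMB chair within 1-2 business days with no causality filter.

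**The concern.** The definition and the ratings apply different tests. A reasonable possibility can exist while another explanation is still more probable; the ratings ask which explanation is ahead. Two investigators could rate the same SAE differently and each point to the text in support.

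Two reporting steps depend on the result: forwarding to the supplier and, for unexpected events, expedited reporting to regulators. The causality judgement in both is the site investigator's. The Medical Monitor reviews every SAE, but the judgement assigned to that role is expectedness, and no power to change the causality rating is stated. Competing explanations are easy to find in this trial. Every patient is scheduled for a procedure, other drugs that affect hemostasis are allowed (sections 7.1 and 7.4), and the population is older with other conditions (section 10.1.1.1).

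**Working it through.** The plan states no figure on this point, so there is none to reproduce. The check sets the wording side by side.

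**1. Apply the definition and the ratings to four cases** (timing does not argue against the drug).

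| Investigator's view of the SAE | Drug-related by the definition? | Rating under the scale |
|---|---|---|
| Drug is the leading explanation | Yes | *Likely related* |
| Drug and an alternative equally likely | Yes | Neither: the alternative is not more likely and not less likely |
| Drug plausible, an alternative likelier | Yes | *Unlikely related* by the comparison of explanations; the first sentence of *Likely related* points the other way |
| No reasonable possibility of drug causation | No | *Unlikely related* |

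Definition and ratings agree in rows 1 and 4. Row 2 has no clear home, and row 3 is contradictory.

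**2. Follow row 3 through reporting.** If it is rated *Unlikely related*:

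- Supplier forwarding (11.1.8): not triggered. Unexpectedness plays no part in this step.
- FDA/Health Canada (11.1.9): not triggered, even if the event is unexpected.
- DSMB chair (11.1.8): still sent, since no causality filter applies.
- Endpoint analyses (5.12.1 to 5.12.4): unchanged. ATE, major and minor bleeding, myocardial infarction, DVT, PE and death are compared by arm without a causality rating.

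**3. Check whether blinding settles the comparison.** Study drug is double-blind (section 5.6). Section 11.1.4 does not say whether the investigator judges causality as if dalteparin had been given or allows for the chance of placebo. The planning rates for major bleeding in 5.11.2, 3.0% with bridging and 1.0% without, show that this matters. Assume 1:1 allocation and no confounding, and take the average share of events caused by the drug:

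- as if dalteparin was given: (0.03 − 0.01) / 0.03 = 0.67, so the drug is the likelier explanation;
- averaged over both arms: (0.03 − 0.01) / (0.03 + 0.01) = 0.50, a tie that the comparison of explanations leaves unrated.

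The same rates give a different rating under each convention. These are averages used for illustration; the plan does not ask investigators to rate individual events this way.

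**The case against.** **The scale leaves room for judgement.** The rating is a case-by-case clinical decision, and the opening sentence of *Likely related* is close to the reasonable-possibility standard. An investigator could rate a row 3 event *Likely related* on that wording. This stands: the text does not force these SAEs out of reporting, so the claim is that they may be missed, not that they will be. It also confirms that *Likely related* contradicts itself.

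**A reader might infer a numerical cut-off,** for example that any SAE that dalteparin doubles would be rated *Unlikely related*. The documents do not support this. A doubling is not a figure in the plan. At a rate ratio of 2 the average drug-caused share is (2 − 1)/(2 + 1) = 33% averaged over arms, but (2 − 1)/2 = 50% if dalteparin is assumed given, and the plan chooses neither convention.

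**A reader might infer that surgery will usually be the likelier cause,** because section 6.3.1 expects about 80-90% of bleeds "to occur at the site of the surgery/procedure". That figure says where bleeding occurs, in a description of dalteparin's own adverse reactions. It does not say that surgery rather than drug is the cause.

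**A reader might infer that expedited bleeding reports would be lost.** Expediting also requires the event to be unexpected. Bleeding is the main listed reaction in 6.3.1, so it would probably fail that condition at any causality rating; the product label that the Medical Monitor uses is not in the documents.

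**A reader might extend the point to NHLBI reports or to SAE tables.** The 7-day NHLBI clause in 11.1.8 and the unanticipated-problem definition in 11.1.6 concern relation to study participation, which is a different judgement. No SAE table by relatedness is specified, so none can be said to be biased.

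**Conclusion.** The inconsistency is real and lies on the face of section 11.1.4. The definition uses reasonable possibility, the ratings use the balance of explanations, the upper rating mixes the two, and an even balance fits neither. The consequence is limited. An SAE with a plausible but not leading drug cause may not be forwarded to the supplier and, if unexpected, may not be expedited to FDA or Health Canada.

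The number of such SAEs cannot be estimated, because the documents give no distribution of SAEs by likely cause. The conclusion assumes that sites apply the comparison of explanations as written and do not rely on the opening sentence of *Likely related*. The point does not touch the primary or secondary comparisons or the flow of SAE reports to the DSMB chair. It is a defect in safety reporting that should be corrected, not evidence that the trial would hide harm from bridging.

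**What to change.** Use one threshold throughout. In 11.1.4, replace the two ratings with, for example:

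- *Related*: there is a reasonable possibility that study drug caused or contributed to the event, even if another cause is also possible or more likely.
- *Not related*: there is no such reasonable possibility.

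Make *Related* the causality trigger in 11.1.8 (supplier) and 11.1.9 (regulators), and leave the separate unexpectedness condition in 11.1.9 as it is. Adding a *possibly related* level would also work, provided that the text states which levels trigger each report. State in 11.1.4 whether the blinded investigator judges causality as if active drug had been given.

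The cost is wording in three sections, one eCRF field, and somewhat more related SAEs to forward and review.

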11.1.7 Follow-up of SAEs

- All SAEs will be followed until resolution, until the condition stabilizes, until the event is otherwise explained, or until the D +37 follow-up visit, whichever occurs first.
- As additional information pertaining to an SAE becomes available, the eSAE form should be updated and resubmitted within 1 business day of knowledge of the information.

11.1.8 DCRI Safety Surveillance and Medical Monitor:

- DCRI Safety Surveillance will be notified of SAEs via email and will print the SAE form from the electronic data capturing system.
- DCRI Safety Surveillance will perform a clinical review of all SAE reports to verify that all sections are complete and consistent.
- DCRI Safety Surveillance will query for incomplete information, data clarification, and/or follow-up information within the Inform database.
- DCRI Safety Surveillance will write a clinical narrative of the event, enter the data into the Clintrace safety database and code the event using the current MedDRA dictionary.
- The DCRI Medical Monitor will review all SAEs, the MedDRA coding and assess the event for "expectedness" per the dalteparin product label.
- DCRI Safety Surveillance will forward the SAE report, a copy of the narrative, a copy of any queries sent to the site, and the Medical Monitor's assessment to [name], and the DSMB chair within 1-2 business days of initial receipt. A copy of the above documents

CONFIDENTIAL

will be forwarded to Eisai for SAEs assessed by the site investigator as "likely related" to study drug.

 SAEs will be reported to NHLBI according to current NHLBI Adverse Event and Unanticipated Problem Reporting Policy. The NHLBI Project Officer will be provided with a copy of the SAE report for all fatal, life-threatening, or unexpected serious adverse events that are likely related to study participation within 7 calendar days. All unanticipated problems will be reported to NHLBI within 30 calendar days.

11.1.9 Regulatory Reporting

All SAEs which are assessed as unexpected by the Medical Monitor and associated with the use of the study drug (likely related) by the Site Investigator require expedited reporting to the FDA and/or Health Canada. For these events, DCRI Safety Surveillance will generate CIOMS forms and forward them to [name] for review and to DCRI Regulatory Services for submission. DCRI Safety Surveillance and Medical Monitor will provide an Investigator Alert packet for distribution to investigative sites.

12.0 Relationship to Institutional Policies on Conflict of Interest

Since existing polices on conflict of interest may vary between participating institutions, it is expected that site investigators will comply with the policies on conflict of interest, which exist within their individual participating institutions. This is the responsibility of each individual investigator.

13.0 Prototype of Informed Consent (see appendix A)

13.1 Patient Withdrawal from the BRIDGE Trial

A patient may be withdrawn from the trial at any time during the study and without prejudice to their subsequent care if the patient, site investigator, or another treating clinician believes it is not in the patient's best interest to continue participation in this trial.

14.0 Regulatory Affairs

The DCRI Regulatory Services group will review the patient education and enrollment materials and the SAE plan. Since this trial will be conducted at Canadian sites, the Regulatory Services group will interact with Health Canada on behalf of the **BRIDGE** trial, and will provide ongoing regulatory guidance to the project team.

15.0 Scientific Reporting and Publication

The results of this trial will have a major impact on patient care, given that up to 400,000 patients are assessed for bridging therapy annually in North America. In accordance with NIH policy, the Executive Committee will be responsible for the scientific reporting, publishing and/or presentation of the trial results. Several strategies will be implemented to broadly disseminate the study results. First, our primary audience will include physicians and other healthcare providers (e.g., pharmacists, nurses) involved in the management of patients on chronic anticoagulant therapy. Providers will be targeted through several organizations, including the Anticoagulation Forum in the U.S. and the Thrombosis Interest Group of Canada.

During the last year of the study, the Executive Committee will hold monthly teleconferences to review upcoming national and international meetings to implement broad dissemination of the study results. It is anticipated that these results will be presented at a Late-Breaking Clinical Trials session at an international scientific meeting (e.g., American Heart Association, American Society of

CONFIDENTIAL

Hematology) and undergo fast-track publication in a major journal. If judged appropriate by the BRIDGE Steering Committee and NIH program staff, a Clinical Alert may be sent to the relevant specialists in internal medicine, hematology, and cardiovascular diseases, as noted above. If the trial results are highly significant, we will work with the NIH to generate a press release to the public concerning the results. The Executive Committee will also seek to promote rapid inclusion of the trial results into consensus reports, such as the ACCP Guidelines for Antithrombotic and Fibrinolytic Therapy, to promote broad dissemination of the results.

- 1. American Heart Association. *Heart Disease and Stroke Statistics Update*. 2001 [cited November 23, 2005]; Available from: http://www.americanheart.org/presenter.jhtml?identifier=1928.
- 2. Douketis, J.D., J.A. Johnson, and A.G. Turpie, *Low-molecular-weight heparin as bridging anticoagulation during interruption of warfarin: assessment of a standardized periprocedural anticoagulation regimen.* Arch Intern Med, 2004. **164**(12): p. 1319-26.
